3.0 METHODOLOGISTS

3.1.1 Study Design

The studies is a mixed, clinical trials and cross-sectional studies.

3.1.2 Sampling Method

Random sampling is used in this study.

3.1.3 Study Location

The study will take place at the Optometry Clinic within the Optometry and Vision Sciences Programme, Faculty of Health Sciences, Universiti Kebangsaan Malaysia. This location was selected due to its status as the primary clinic for optometry practice within the Faculty of Health Sciences, equipped with all necessary equipment for the study. Situated centrally within the Faculty of Health Sciences, it offers convenient access for undergraduate subjects participating in the study.

3.1.4 Study Sample Calculation

The sample size for this study was determined using the Daniel formula (1999), with a total of 10% of the overall sample size allocated for the study. Considering a dropout rate of 10%, a total of 18 subjects were required for the study.

$$n = \frac{Z^2 P(1-P)}{d^2}$$

$$n = \frac{(1.96) (0.3)(1-0.3)}{(0.05)^{-2}}$$

$$n = \frac{0.4116}{0.0025}$$

$$n = 164.64$$

$$n \text{ study} = 10\% \text{ x } 164.64$$

$$= 16.46$$

$$= 16$$
Dropout rate = 10% x 16
$$= 1.6$$

$$= 2$$
Total subjects = 16 + 2

= 18 subjects

n = required sample size

= 1.96, the value of Z when the confidence level is 95% Z^2

P = 0.3, prevalence of contact lens clinic patients at UKM Optometry Clinic in semester 2, session 2022/2023

d = 0.05, margin of error

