3.1.10 Flow Chart

3.1.11 Data Analysis

The forthcoming study will employ IBM SPSS Statistics Version 27 for data analysis. The normality of the data will be assessed utilizing the Shapiro-Wilk test. Subsequently, the distribution of the data will be examined accordingly.

Utilize the Paired t-test for normally distributed data or the Wilcoxon signed-rank test for non-normally distributed data to assess the disparities in tear quality and quantity before and after
 Employ the Paired t-test for normally distributed data or the Wilcoxon signed-rank test for non-normally distributed data to compare the mean quality and quantity of tears between FDA contact lens application groups I and II, groups III and IV, as well as silicone hydrogel materials A and B.

iii. Employ the Paired t-test for normally distributed data or the Wilcoxon signed-rank test for non-normally distributed data to assess the comfort levels associated with the application of FDA contact lenses within groups I and II, groups III and IV, as well as silicone hydrogel materials A and B.

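### The sample size of 18 comes from a prevalence formula with Z left unsquared and the result cut to a tenth, so it neither meets its own precision target nor sizes any planned comparison

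*Protocol*

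**What the plan says.** Section 3.1.4 of the Protocol uses the standard formula for estimating a single proportion, n = Z²P(1−P)/d². Its inputs are:

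- Z: "1.96, the value of Z when the confidence level is 95" percent.
- P: "P = 0.3, prevalence of contact lens clinic patients at UKM Optometry Clinic in semester 2, session 2022/2023".
- d: "d = 0.05, margin of error".

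The worked lines divide 0.4116 by 0.0025 to give 164.64. The section then takes a tenth of this, described as "with a total of 10% of the overall sample size allocated for the study", which gives 16.46, rounded to 16. Ten percent of 16 is added as 2, and the section concludes: "Considering a dropout rate of 10%, a total of 18 subjects were required for the study".

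Section 3.1.11 plans paired t-tests or Wilcoxon signed-rank tests. These assess tear quality and quantity before and after wear, and they are also used "to compare the mean quality and quantity of tears between FDA contact lens application groups I and II, groups III and IV" and between the two silicone hydrogel materials. Comfort is compared within the same three lens pairs. The Protocol gives no target difference, standard deviation, power or significance level for any of these tests.

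**The concern.** This is the Protocol's only justification for its sample size, and it fails in three separate ways: the arithmetic does not follow the printed formula, the result is cut tenfold without a reason, and the quantity being estimated is not one that the trial studies.

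A reader of section 3.1.4 would take 18 to be the number needed for 95% confidence and a 5-point margin. It is not, and nothing in the section shows what 18 subjects can detect in the tests that will be run. This matters more because the research hypothesis in section 2.4 is worded as no significant disparity. With few subjects and no stated detectable difference, a non-significant result could be taken as support for that statement when the trial had little chance of finding a moderate difference.

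**Working it through.** **1. Reproducing the stated figure.** Inputs from section 3.1.4: Z = 1.96, P = 0.3, d = 0.05, so P(1−P) = 0.21 and d² = 0.0025.

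- 1.96 × 0.21 = 0.4116, and 0.4116 / 0.0025 = 164.64
- 10% of 164.64 = 16.46, rounded to 16
- 10% of 16 = 1.6, rounded to 2, and 16 + 2 = 18

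The 18 is reproduced exactly, but only with 1.96 unsquared. (In the substituted line the exponent on 0.05 reads as −2. This may come from the text extraction and has no effect, since the next line uses 0.0025.)

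**2. The formula as printed.**

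- 1.96² = 3.8416
- 3.8416 × 0.21 = 0.8067
- 0.8067 / 0.0025 = 322.7, which is 1.96 times the stated 164.64

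**3. The margin that each number delivers.** The 95% half-width is 1.96 × √(0.21/n):

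| n | 95% half-width (percentage points) |
|---|---|
| 164.64 | 7.0 |
| 18 | 21.2 |
| 16 | 22.5 |
| stated target | 5 |

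Even without the 10% step the target is missed. With it, the margin at 16 subjects is about 4.5 times the stated one (22.5 / 5). The tenfold cut does far more damage than the unsquared Z, which is a factor of 1.96.

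**4. What 16 complete pairs give for the planned tests.** The Protocol states neither a significance level nor a power for these tests. I assume a two-sided 5% level and one unadjusted paired t-test. Effects are in SDs of the paired differences, and power comes from the noncentral t distribution with 15 degrees of freedom and noncentrality effect × √16.

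- 80% power: effect 0.75 SD
- 90% power: effect 0.87 SD
- Power at 0.5 SD: 46%
- Power at 0.3 SD: 20%
- 95% confidence interval half-width: t(0.975, 15)/√16 = 2.131/4 = 0.53 SD

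If all 18 complete, the effect for 80% power falls only to 0.70 SD. On the same assumptions, 80% power needs 15 subjects at 0.8 SD, 34 at 0.5 SD and 90 at 0.3 SD.

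**5. Effect of several tests.** Section 3.1.11 implies nine between-lens comparisons (tear quality, tear quantity and comfort, each for three lens pairs). Were a Bonferroni adjustment over nine applied (my assumption; the Protocol plans none), power at 0.75 SD would be 44% and the effect for 80% power would be 1.04 SD.

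**The case against.** The errors themselves have no good defence. Damage from text extraction cannot explain the unsquared Z, because 0.4116, 0.0025 and 164.64 are legible and agree with one another. A separate analysis plan would not cure it either, since the Protocol states its own calculation and that calculation is wrong. The serious objections concern emphasis and remedy.

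- *Eighteen may be enough for a within-subject design.* It may, if the true differences are about 0.7 to 0.75 SD or larger. The Protocol does not make that argument and gives no SD or meaningful difference for the Schirmer test, NIBUT or the comfort score from which to make it. Whether 18 is adequate therefore cannot be judged from the document. Keeping 18 is acceptable only as a declared feasibility number.
- *The 0.75 SD figure is favourable.* This stands. It applies to one unadjusted t-test; it does not cover the Wilcoxon alternative or multiple testing. It should be labelled accordingly.
- *The margin of 0.05 is an input, and the 10% step is stated openly.* This also stands. The Protocol does not say outright that 18 subjects achieve a 5-point margin. The accurate criticism is that its inputs do not carry through to the number it calls required.
- *The null-hypothesis wording is conventional, and no equivalence claim is planned.* True. The risk of reading non-significance as no difference is one of interpretation, and a sentence in the Protocol can prevent it.

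**Conclusion.** The point holds in all three parts. By its own formula the Protocol should have obtained 322.7, not 164.64. After the unexplained cut, 16 to 18 subjects give a 95% margin of 22.5 to 21.2 points instead of 5. The proportion in the formula is one that no objective or analysis estimates, so none of the planned paired comparisons is sized.

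Parts 1 and 2 rest only on figures in section 3.1.4. The power figures (80% at 0.75 SD, 46% at 0.5 SD, confidence interval half-width 0.53 SD) assume 16 complete pairs and a single two-sided 5% paired t-test. Correcting Z alone would not repair the section: 322.7 answers a question the trial does not ask and should not be read as a recommended size. Because this is the sole basis for the trial's size and it is wrong as written, it must be fixed.

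**What to change.** In section 3.1.4, delete the prevalence formula, the 10% step, and the confidence level and margin attached to them. State that 18 enrolled, with 16 expected to complete, is a feasibility number, and say what it delivers: for a single paired t-test at two-sided 5%, 80% power for a within-subject difference of 0.75 SD of the paired differences, with a 95% confidence interval half-width of 0.53 SD. Say that this figure allows neither for multiple comparisons nor for the Wilcoxon alternative. If the investigators have an SD and a meaningful difference for the Schirmer test, NIBUT or the comfort score, they should set these beside the 0.75 SD so that readers can judge whether it is small enough.

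In section 3.1.11, add that each comparison will be reported with its estimate and confidence interval, and that a non-significant result will not be presented as evidence of no difference.

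The cost is one rewritten section and one added sentence. Enrolment and the planned tests do not change. The price is that the stated case for the sample size becomes visibly weaker: the trial can reliably detect only large differences.

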3.1.5 Subject

UKM undergraduate students' Kuala Lumpur Campus was chosen as the subject of study because the location of the study was at the UKM Optometry Clinic located at the Kuala Lumpur Campus of UKM.

3.1.6 Participation Criteria

- 1. Healthy volunteered individuals between 19 and 29 years old.
- 2. Individuals with a refraction power of less than -6.00 spherical diopters and astigmatism power of less than -1.00 cylindrical diopters.
- 3. Experienced contact lens wearers. (Participants are asked to lay off contact lenses for at least 2 weeks before the clinical trial starts (McKernan et al., 2014))

3.1.7 Exclusion Criteria

- 1. Individuals who smoke (Ward et al. 2010)
- 2. Individuals with history of diseases on the ocular surface, ocular trauma, refractive surgery, intraocular and extraocular surgery.
- 3. Pregnant individuals (Yenerel &; Kucumen, 2015).
- 4. Individuals taking systemic drugs that can cause dry eyes (Fraunfelder et al. 2012).

3.1.8 Instruments

- 1. Hydrogel soft contact lenses Group I, II, III, IV, Va and Vb
- 2. Schirmer Strip
- 3. Fluoresine Strip
- 4. Saline solution
- 5. Multipurpose solution Maxvue
- 6. Slitlamp Biomicroscope
- 7. Bausch & Lomb Keratometer
- 8. Contact Lens Discomfort Index Questionnaires (CLDI)

3.1.9 Study Protocol

Participants for this study will be recruited from among UKM undergraduate students at the Kuala Lumpur Campus based on the inclusion and exclusion criteria. Recruitment of volunteers will be conducted through advertisement. Simple random sampling will be used for participant selection, with those meeting the inclusion criteria being eligible for the study, while those meeting the exclusion criteria will be dismissed.

Before the commencement of the clinical trial, all participants will be provided with a consent form to review. The study will take place at the UKM Optometry Clinic, [name], Kuala Lumpur, Malaysia.

Participants will be required to attend the UKM Optometry Clinic for three sessions, each lasting 8 hours, during which they will wear FDA hydrogel contact lenses (groups I, II, III, IV, Va and Vb). Each lens will be placed on one eye only. Hence, the study will involve three wearing sessions, with the first session focusing on groups I and II FDA contact lenses, the second session on groups III and IV FDA contact lenses, and the third session on hydrogel silicone contact lenses Va and Vb. A 2-week rest period will be provided between each session. The complete study procedure is outlined as follows:

Care for Contact Lenses Leaflet.

Ensuring proper hygiene and technique is crucial to prevent eye health complications while wearing contact lenses. Subjects will receive thorough guidance on essential practices, including: maintaining hygiene care, correctly utilizing contact lens solution, applying and removing contact lenses, and adhering to permissible actions during wear. Additionally, subjects will be provided with a hotline for any inquiries or emergencies arising during contact lens use. Furthermore, they will receive a pamphlet titled "Soft Contact Lens Instructions" available at the UKM KL Optometry Clinic.

[figure not shown]

Figure 1 & 2. Soft contact lens use instructions

Pre-Assessment

A pre-assessment will precede the contact lens application during the initial session. The parameters measured will include these three tests: a) assessment of tear quantity using the Schirmer Test, b) evaluation of tear quality with the NIBUT Test, and c) examination of corneal staining using the Efron Grading Scale. These same tests will be conducted after the contact lenses have been worn for 8 hours and subsequently removed.

a) Tear Quantity Assessment (Schirmer Test)

To assess tear quantity, the Schirmer test will be employed using a 5mm x 30mm Schirmer strip. The strip will be positioned in the temporal area of the subject's lower eyelid. The subject will be instructed to look upwards and blink naturally for 5 minutes, after which the Schirmer strip will be removed. The length of the wet portion of the strip will be measured and documented. Three readings will be obtained in millimeters (mm), and the average reading will be calculated for data analysis (Kallarackal et al., 2002).

b) Tear Quality Assessment (NIBUT Test)

The assessment of tear quality was conducted using the Non-Invasive Break Up Time Test (NIBUT) technique with the Bausch & Lomb keratometer. The subject was instructed to rest their

chin on the designated chin rest and align their forehead with the headrest. Initially, the subject blinked several times and then refrained from blinking. Time was measured from the last blink until the appearance of any distortion or break in the "mires." This time interval was recorded as the NIBUT measurement. If the subject blinked during the measurement, the test was paused briefly, and resumed after a few blinks. A one to two-minute break was provided between each measurement. Three readings were taken, and the average of these readings was utilized for subsequent statistical analysis (Mohidin et al., 2002).

c) Corneal Coloring Assessment (Efron Grading Scale)

The evaluation of corneal staining will involve using the Efron Grading Scale to assess any marks or damage on the subject's cornea before applying contact lenses. Initially, fluorescein dye will be applied to the subject's eyes using fluorescein strips moistened with saline solution. The subject will be instructed to look up, and the moistened fluorescein strip will be gently touched to the lower eyelid, followed by blinking. Using a biomicroscopic slit lamp equipped with a blue cobalt light, any staining or markings on the cornea will be examined. Any observed findings will be documented according to the Efron Grading Scale. Subsequently, the subject's eyes will be rinsed with saline solution to remove the fluorescein dye. The cornea will be divided into five zones (central, superior, inferior, temporal, and nasal) for recording observations, as depicted in Figure 1. The Efron Grading Scale, recognized for its suitability in assessing corneal coloring, will guide the evaluation process (Dundas et al., 2001; Woods & Fonn, 2018).

[figure not shown]

Figure 3. Grading Scale Based on 5 Corneal Zones

i. Contact lens application

The placement of group I FDA contact lenses will occur on one side of the subject's eye, while group II FDA contact lenses will be positioned on the opposite side, with the positioning being randomized and unknown to the subjects. Researchers will delicately insert the contact lenses, providing clear instructions and precautions to the subjects regarding their wear. Subjects will be advised to remain near the UKM KL Campus throughout the contact lens application and return to the UKM Optometry Clinic after 8 hours for lens removal. Additionally, subjects will be instructed to promptly notify the researcher of any discomfort, pain, or unforeseen issues related to the wearing of contact lenses.

ii. Post-Wear Assessment

The researcher will remove the contact lenses from the subject's eyes. Subsequently, a postwearing examination of the contact lenses will be conducted. This examination mirrors the preuse assessment and includes a) evaluating tear quantity using the Schirmer Test, b) assessing tear quality with the NIBUT Test, and c) grading corneal staining based on the Efron Grading Scale. Following the removal of contact lenses, subjects will be required to complete the Contact Lens Discomfort Index (CLDI) questionnaire twice at each appointment: once for the right eye and once for the left eye. This allows for the measurement of comfort levels separately for each eye.

d) Contact Lens Discomfort Index Questionaires (CLDI)

The CLDI questionnaire will be employed to evaluate the comfort level during the usage of Group I and II FDA contact lenses. This questionnaire's selection of questions is rooted in the Contact Lens Dry Eyes Questionnaire (CLDEQ)-8. Known for its robustness and reliability, the CLDI questionnaire is specifically crafted to gauge comfort levels associated with contact lens wear (Arroyo-del Arroyo et al., 2022).

English version of the contact lens discomfort index (CLDI)

The Contact Lens Discomfort Index (CLDI) questionnaire is an easy instrument to measure the level of discomfort with the contact lenses.

Note: questions highlighted in grey correspond to the subscale score.

- Please, answer the following questions.
- 1. Since you have been wearing this type of contact lens, have you always worn them the same number of hours per day?
 - I currently use them more than previously (0)
 - I use them the same amount as previously (1) I use them fewer hours per day than I previously did because I prefer to or because it was recommended to me (1)
 - I use them fewer hours per day due to dryness and/or discomfort (2)
- 2. Do you wear these contacts as many hours as you wish/need to?
 - Yes (0)
 - □ No (1)
- 3. Do you USUALLY wear contact lenses while using electronic devices/video display terminals?
 - □ No (respond to question 4.1) (0)
 - □ Yes (respond to question 4.2) (0)

- 4.1 If you do NOT use your contact lenses when using electronic devices/video display terminals, what is the reason? (you can select multiple responses)
 - Because I don't feel like it (0)
 - Because I don't see well or my eyes become red (0) Because they bother me or I notice dryness (1)
- 4.2 If you DO use contact lenses while using electronic devices/video display terminals, do you USUALLY notice discomfort with them?
 - No (0)
 - No (0)
 Yes (1)
- 5. Do you USUALLY notice problems with these contact lenses when in dry environments (air conditioning or heat), with low humidity or in the wind?
 - No (0)Yes (1)
- 6. Answer the following question by checking the box that best represents your response (only check one box per symptom). During a typical day in the past week, have you experienced any of the following symptoms?

	No, I have not experienced it (0)		rienced it only while contact lenses (1)	Yes, I experienced it both with and without contact lenses (2)				
Dryness								
Discomfort								
During a typical day in the past week, have you experienced any of the following symptoms both with and without contact lenses on? (you can select multiple options)		 8. Describe the level of discomfort right b removing your contact lenses. No discomfort (0) Somewhat uncomfortable (1) 						
 Red eyes (1) Itching (1) 				ortable (2) comfortable (3)				
 Poor vision (1) Watery eyes (1) 		 Describe your overall satisfaction with the use o these contact lenses. 						
None (0)			 Very satisfied Not satisfied 					

Figure 4. Contact Lens Discomfort Index (CLDI) Questionnaire

[figure not shown]
i. Rest Period

[figure not shown]
A "washout period," also known as a rest period, lasting for two weeks will be provided to the subjects to prevent any unauthorized observations.

ii. Second and Third Appointments

Subjects will be required to attend a second appointment following a rest period for the application of group III and IV FDA contact lenses. This appointment will involve the repetition of the procedure, including pre-application examination, contact lens wear, post-use examination, and subsequent rest period. The same procedure will be replicated for a third appointment involving the wearing of silicone hydrogel contact lenses Va and Vb.

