Differences in water content within soft contact lenses may contribute to corneal dehydration, leading to dryness in the eyes. Despite advancements in soft contact lens manufacturing, instances of corneal allergies or sensitivities to such lenses have been reported (Moreddu et al., 2019). Studies suggest that changes in the tear film may occur within the first hour of contact lens wear, but quantitative data on tear film thickness post-application is lacking (Nichols et al., 2004).

Furthermore, there is limited data available for tear assessment, corneal staining, and comfort levels among FDA contact lens groups I, II, III, and IV, with recent studies predominantly focusing on silicone hydrogel lenses. Therefore, this study aims to compare tear quality and quantity, as well as comfort levels, between these contact lens groups and silicone hydrogel lenses.

While tear assessment before and after wearing silicone hydrogel lenses may reveal significant changes, no substantial differences are observed between different silicone hydrogel materials. However, factors such as water content, material composition, wearing duration, and lens deposition are more closely associated with corneal staining than contact lens care solutions, ocular surface characteristics, tear composition, demographics, or medical factors (Nichols & Sinnott, 2011).

In response to consumer needs, advancements in contact lens technology continue, with efforts aimed at enhancing wearer comfort. Innovations such as the incorporation of wetting agents, hydrophilic monomers, surface treatments, and water gradient surface technology are introduced to mitigate the impact of wearing silicone hydrogel lenses on the tear layer (Sulley & Dumbleton, 2020). Therefore, ongoing research into technological and material developments in contact lens manufacturing is essential to understand their effects on consumers and to facilitate future improvements.

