2.5 Conceptual framework

Figure 1 illustrates the conceptual framework for assessing tear quantity, corneal staining, and comfort levels during the wear of FDA contact lenses Group I, II, III, IV, and V materials.

2.6 **Objectives**

2.6.1 General Objectives:

The objective is to examine the impact of FDA contact lenses Group I, II, III, IV, and silicone hydrogel on tear assessment, corneal staining, and comfort levels among undergraduate students at UKM Kuala Lumpur Campus.

2.6.2 Specific Objectives:

i. Assessing tear quantity, corneal staining, and comfort levels before and after 8 hours of wearing FDA contact lenses Group I, II, III, IV, and silicone hydrogel.

ii. Contrasting tear evaluation and corneal staining pre- and post-8-hour application of FDA contact lenses Group I, II, III, IV, and silicone hydrogel.

iii. Comparing comfort levels pre- and post-8-hour wear among FDA contact lenses Group I,II, III, IV, and silicone hydrogel (Va and Vb).

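### Every subject wears the lens pairs in the same session order, so the stated comparison of hydrogel with silicone hydrogel lenses cannot be separated from visit

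*Protocol*

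**What the plan says.** Section 3.1.9 sets three wearing sessions two weeks apart, with "the first session focusing on groups I and II FDA contact lenses, the second session on groups III and IV FDA contact lenses". The paragraph on later appointments confirms the last step: "The same procedure will be replicated for a third appointment involving the wearing of silicone hydrogel contact lenses Va and Vb". No section randomises or balances the order of the sessions. The only random allocation of lenses is which eye receives which lens of the pair, "with the positioning being randomized and unknown to the subjects".

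The aims reach across sessions. Section 2.2 says that "this study aims to compare tear quality and quantity, as well as comfort levels, between these contact lens groups and silicone hydrogel lenses". Objective iii in section 2.6.2 reads "Comparing comfort levels pre- and post-8-hour wear among FDA contact lenses Group I,II, III, IV, and silicone hydrogel (Va and Vb".

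The between-lens tests in section 3.1.11 are narrower. For tears they compare I with II, III with IV, and silicone hydrogel material A with B. For comfort the plan is likewise to "assess the comfort levels associated with the application of FDA contact lenses within groups I and II, groups III and IV", and within the silicone hydrogel pair.

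Two measurement details matter. The pre-wear examination is repeated at later visits: "This appointment will involve the repetition of the procedure, including pre-application examination, contact lens wear, post-use examination, and subsequent rest period". The comfort score has no pre-wear value: "Following the removal of contact lenses, subjects will be required to complete the Contact Lens Discomfort Index (CLDI) questionnaire twice at each appointment".

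**The concern.** Groups I and II are seen only at visit 1, III and IV only at visit 2, and Va and Vb only at visit 3. Anything that changes between visits therefore changes together with the lens pair. Examples are the examiner's grading level, the subjects' familiarity with the tests and the questionnaire, and conditions on the day. A difference between hydrogel and silicone hydrogel lenses could then be a visit effect, and a real difference could be masked by one. The same holds for I/II against III/IV.

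Comfort is the most exposed outcome. For tears and staining, the change from the same-visit pre-wear value removes a shift in level between visits, though not a visit effect on the 8-hour change itself. The CLDI offers nothing to subtract. Each subject completes it twice per appointment, so by the third session each has already completed it four times, always for hydrogel lenses.

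**Working it through.** **Inputs from the protocol.** 18 subjects, of whom 16 are expected after dropout (section 3.1.4); six lenses in three fixed pairs; one lens per eye; three sessions; eye randomised within a session (section 3.1.9). The protocol gives no variance and no figure for drift between visits.

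**1. What can be estimated.** Take a linear model with subject, lens and eye terms on 18 × 6 = 108 observations.
- Rank without session: 18 (subjects) + 5 (lenses) + 1 (eye) = 24.
- Add two session columns under the fixed order. The session 2 column equals the sum of the III and IV columns, and the session 3 column equals the sum of the Va and Vb columns. The rank stays at 24, so session is fully aliased with lens pair.
- Six lenses give 6 × 5 / 2 = 15 pairwise contrasts. With session in the model, 3 are estimable (I–II, III–IV, Va–Vb). The other 12 are not, nor is the pooled hydrogel vs silicone hydrogel contrast.
- With three subjects on each of the six session orders, the rank is 24 + 2 = 26. All 15 contrasts and the pooled contrast are then estimable.

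**2. Bias from a steady drift.** Let the visit effects be 0, δ and 2δ, with no true lens difference.
- Silicone hydrogel minus mean hydrogel: 2δ − (0 + δ)/2 = 1.5δ.
- III/IV minus I/II: δ − 0 = δ.
- Silicone hydrogel minus I/II: 2δ − 0 = 2δ.
- Within any session, both eyes carry the same visit effect, which cancels in the paired difference.

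For the CLDI, δ is drift in the score itself. For tears and staining analysed as change, δ is only drift in the 8-hour change.

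**3. Illustration only.** Assume a cross-session paired t test, which the protocol does not list, with 16 completers (15 df), two-sided 5%, and δ expressed in SDs of the contrast. The noncentrality is 1.5δ × √16.

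| Assumed δ | Standardised bias 1.5δ | Noncentrality | False-positive rate |
|---|---|---|---|
| 0.1 | 0.15 | 0.6 | 8.7% |
| 0.2 | 0.30 | 1.2 | 20.3% |
| 0.3 | 0.45 | 1.8 | 39.2% |

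**4. Precision cost of balancing.** Work on session means (average of the two eyes), in units of their residual variance.
- The contrast, session mean on silicone hydrogel minus the average of the two hydrogel session means, has variance (1 + 1/4 + 1/4)/18 = 1.5/18 = 0.0833. This is the same with and without adjustment for session when the six orders are balanced.
- Residual df: 54 − 18 − 2 − 2 = 32.
- If two subjects are lost, a perfectly balanced 16 would give 1.5/16 = 0.09375. Over all 153 ways of losing two of 18, the variance runs from 0.0941 to 0.0952, at most 1.6% higher (0.09524/0.09375 = 1.016), with 48 − 16 − 2 − 2 = 28 residual df.

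**The case against.** The strongest reply is that no listed analysis is affected. Every between-lens test in section 3.1.11 is made within a session, and the pre/post tests compare values around the same wear period. This is right. The fault lies in a stated aim that the design cannot answer, not in a biased listed test.

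Second, the cross-session aim has a narrow textual basis. The research question, the hypothesis and objectives i and ii are framed as before against after wear, and objective iii could be read as pre/post within each group. Objective iii is indeed ambiguous, although its most natural reading includes a comparison across groups. The sentence in section 2.2 is not ambiguous.

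Third, aliasing shows that a visit effect could not be separated, not that one exists. The two-week rest, experienced wearers, a single clinic, masking of lens position and repeated pre-wear examinations limit some sources of drift. That is fair, and it is why the false-positive range above carries no evidential weight. But the rest addresses carryover rather than visit, and none of these features removes a visit effect on the 8-hour change or on the CLDI. A cross-session conclusion would rest on an assumption of no visit effect that the data cannot test. A separate analysis plan cannot repair this, because no model separates two identical variables.

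Two smaller points stand. Section 3.1.9 first places the pre-assessment in the initial session and only later says that it is repeated. If it were not repeated, tears and staining would lose their partial protection too. The 1.6% figure covers loss of whole subjects, not single missed sessions.

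**Conclusion.** The concern holds. Under the fixed order, hydrogel vs silicone hydrogel and I/II vs III/IV are completely confounded with visit, and 12 of the 15 pairwise lens comparisons cannot be attributed to the lens without assuming that there is no visit effect. This follows from the structure of the design and does not depend on any assumed variance. The size of the resulting error does depend on the drift, which is unknown: 1.5δ for the main contrast.

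The three within-session comparisons stand. As designed, the trial supports those three only, which is less than section 2.2 claims and less than objective iii most naturally means. This should be fixed before the first session, because it cannot be repaired after data collection.

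**What to change.** Keep the three lens pairs, the eye randomisation and the two-week rest. Randomise subjects in balance to the six possible session orders, three per order for 18. In section 3.1.11, add one pre-stated cross-session comparison with subject and session terms, run for each outcome. Use the change from the same-visit pre-wear value for tears and staining, and the post-wear score for the CLDI. State how ordinal or clearly non-normal outcomes will be handled in it, and make clear in section 3.1.9 that the pre-wear examination takes place at every visit.

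The cost is a randomisation list, all six lenses in stock from the first visit, the added model for each outcome, and a minor protocol and ethics amendment. No extra subjects, visits or tests are needed, and the loss of precision is negligible.

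If the order cannot be changed, remove the cross-session aim from section 2.2, reword objective iii in section 2.6.2, and limit the conclusions to I vs II, III vs IV and Va vs Vb, which section 3.1.11 already tests.
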